We will quantify overground walking ability using the 10MWT.⁴⁹ Subjects will perform 2 trials each of the 10MWT at their fastest but safe speed with a minimum of 1-minute rest between trials. Average speed across the two 10MWT trials will be used for analyses. The validated assessment tool will provide an indication of return of our subject population to pre-morbid activities following the initial neurological insult. The 10MWT has high inter-rater reliability, and the rating procedure can be accomplished in approximately 30 minutes.

The screening and physical assessment procedures will last approximately 1.5 hours.

To ensure safety, we also will assess pain, spasticity, systemic hypertension, and autonomic dysreflexia prior to and following caffeine and AIH interventions. We routinely measure pain, spasticity, and incidence of hypertension and autonomic dysreflexia as part of our study protocols in persons with chronic SCI.^{32, 33} We will make measurements at baseline, after session 5, and one-week follow-up, and again at two-weeks follow-ups.

Quantify pain: We will assess pain severity using the Wong-Baker FACES scale of 0 (no pain) to 5 (extreme pain).^{59, 60}

DETAILED STUDY PROTOCOL

Quantify spasticity: We will assess spasticity using the Spinal Cord Assessment Tool for Spastic Reflexes (SCATS).⁵⁸ We will quantify total lower extremity spasticity score using the cumulative sum of 3 SCATS subscales: clonus (0=no spasticity; 3=severe), flexor (0=no spasticity; 3=severe), and extensor (0=no spasticity; 3=severe).

Quantify systemic hypertension incidence rate: In addition to monitoring during the intervention, we will measure systolic and diastolic BP at baseline, after sessions 5, and again at follow-ups. We will define a systemic hypertensive event as a systolic pressure exceeding 140 mmHg and/or diastolic pressure exceeding 90 mmHg.^{46, 47}

We will compute hypertension incident rate for each intervention group as the number of hypertensive events divided by the total person-time. We define person-time in units of person-measures (the sum of the total number of BP measurements) taken for each person. Person-measures accounts for the total number of chances for detecting a hypertensive event and accounts for measurements not made due to drop-out or a disqualifying adverse event.⁶³ Finally, we will compute Relative Risk for each Aim as the incidence rate in the dAIH groups over the incidence rate in the dSHAM groups.⁶⁴

Quantify autonomic dysreflexia incidence rate: We will assess the occurrence of autonomic dysreflexia in all intervention groups. Systolic blood pressure (SBP) will be measured as detailed in common methods. We will assess SBP at baseline, and before, during and immediately after breathing interventions, and again at follow-ups. Additional SBP measurements will be made if participants first present with symptoms characteristic of autonomic dysreflexia (e.g., headache, diaphoresis, blurred vision). An autonomic dysreflexia event will constitute a participant having a SBP increase from baseline of 20 mmHg or SBP greater than 150 mmHg with complaints of headache, diaphoresis, and/or blurred vision and will be diagnosed by our study team clinicians (physicians and physical therapists). An autonomic dysreflexia event will result in termination of study participation and require prompt evaluation by the team physicians and emergency medical team.

We will compute autonomic dysreflexia incident rate for each group as the number of autonomic dysreflexia events divided by the total person-time. We define person-time in units of person-days (the number of days a person remains in the study). Person-days accounts for the total number of chances for detecting autonomic dysreflexia and accounts for days on which measurements were not made due to drop-out or a disqualifying adverse event.⁶³ Finally, we will compute Relative Risk as the ratio of incidence rates between groups.⁶⁴

We previously demonstrated that daily exposures of AIH (up to 5 consecutive days) do not elicit adverse clinical events in persons with chronic SCI.^{32, 33} Similarly, rodents exposed to daily exposure for 7 consecutive days did not induce hippocampal cell death, changes in body mass, or hypertension,^{8, 9} including in animals early after injury.⁸ Determining whether dAIH or in combination protocols lead to the onset of significant pathology (pain, spasms, hypertension, autonomic dysreflexia) in persons with SCI is essential for establishing safe delivery of caffeine combined with AIH in this earlier stage of injury.

Quantify inflammation: We will quantify inflammation using measures of C-reactive protein concentrations in the blood.

- Participant retention plans: Whether or not you complete the whole study, we will pay you \$25 for each visit you do complete. We will also reimburse for up to \$100 per visit in travel

DETAILED STUDY PROTOCOL

expenses. Receipts for travel expenses are required. If eligible, we will reimburse for up to \$150 per night for up to 12 nights in lodging expenses. Receipts for lodging expenses are required. Eligibility depends on travel distance of more than 60 miles to Spaulding Hospital.

19. Data management

Research materials will consist of data from human subjects including: (1) recordings of subject muscle activity, kinematics, and kinetics during overground walking (2) subject anthropometric measurements; (2) video images of the experiments; (3) biological (i.e., blood, saliva) samples; and (4) personal health information collected during screening. Assessment scores will be obtained during an initial screening conducted by the team physician ([name]) and physical therapist.

The clinical and physiological data will be obtained only for research purposes. Upon enrollment, study subjects will be assigned an ID number. The ID number will identify data in reports, public or private, and personal information kept confidential. Data will not be labeled with subject names; no code sheets or linkages between subject name and code number will be made on data collection sheets. Biological samples will be collected, de-identified, and immediately stored according to biohazard safety protocols. Testing results will not be provided to the subjects.

Consent forms and HIPAA waivers that contain subject names will be stored separate from data sheets in a locked file cabinet in the PI's laboratory. Coded data, which include computer files and computer video records, will be kept on a password protected local network in a secured lab area. Any forms/computer files containing the subject's personal information and their ID number will be housed in a locked office/laboratory space and accessed only by the investigators or other study personnel unless required by law. Study records can be opened by court order or produced in response to a subpoena or a request for production of documents unless a Certificate of Confidentiality is in place for this study.

20. Statistical methods

All data will be managed using REDCap⁶⁵, MS 365 Excel 16.54 (Microsoft, USA), and MATLAB R2020a (Mathworks Inc, USA) and will be analyzed using SPSS[®] Statistics 26 (64-bit edition, IBM, USA). Descriptive statistics, including means, standard deviations and 95% confidence intervals of the within-participant pre-post change for each intervention will be calculated for all measures. The baseline characteristics of the participants will be compared using parametric and non-parametric inferencing.

Hypothesis testing: To evaluate our main hypothesis that caffeine prior to AIH enhances walking recovery, we will perform a linear mixed model with fixed effects at a significance at the p=0.05 level.⁶⁶ Intervention (caffeine+dAIH, caffeine+SHAM, placebo+dAIH) and time (day) will be the fixed main effects, with subject as random effect and walking speed (10MWT) as repeat measures. Differences from BL will be compared between and within interventions at D₅, F₁, and F₂. Bonferroni corrections will be made for multiple comparisons. If distributions are not normal, we will perform comparable nonparametric tests. If baseline measures are significantly different between sessions (interventions), an analysis of co-variance (ANCOVA) will be used to analyze the data. We predict walking speed (10MWT) will be greater after daily caffeine+AIH as compared to after daily placebo+AIH and daily caffeine+SHAM.

Blinding integrity analysis: we plan to rigorously quantify blinding integrity here. We will ask participants and raters to guess the intervention received at the end of each intervention and indicate guess confidence using a Likert scale.^{67,68} We will use a contingency table and Fischer's

DETAILED STUDY PROTOCOL

Exact Test to determine if the probability of correct guessing is different from chance. Using multivariate logistic regressions, we also will assess factors that may influence guessing (i.e., adverse events, perceived effects, and sensorimotor changes). In the event of a medical emergency, we will unblind the PI, study participants, and care provider. We also will notify IRB of treatment allocation during adverse event reporting as necessary.

V. Monitoring

21. Data monitoring

While this study is not under FDA review, all investigators have completed/will complete training requirements at Spaulding Rehabilitation Hospital. Staff training will include Protection of Human Subjects that will familiarize our team with updates to Good Clinical Practices (i.e., CITI certification), and other principles related to the ethical and appropriate conduct of clinical research. The Principal Investigator will regularly review study procedures with the Medical Monitor (monthly) and study staff (bi-weekly), and annual reviews will be conducted by the sites' Office of Clinical Research to ensure compliance with applicable regulations. The monitoring plan will include review of elements required by U.S. 21 CFR 50 and ICH E6, Section 4.8. Onsite monitoring visits will be conducted annually. Adverse event reporting and corrective actions will be reported to the Institutional Review Boards and DOD Sponsor as soon as possible to ensure participant safety.

The PI ([name]) will be responsible for monitoring the completeness of all data and source documents. The Principal Investigator will monitor the informed consent procedures in accordance with the Informed Consent Compliance Checklist of Partners HealthCare Systems. Subject data/protocol adherence will be monitored by the research coordinator at each step in the study including.

22. Harms

Checklists and note pages are used to note any deviations or omissions from the protocols. Any clinical/health related issues would be immediately presented to the subject to determine appropriate notification (i.e., current physician or appropriate specialist). Based on the seriousness of the situation Drs. [name] or [name] may be contacted to provide clinical guidance on the appropriate course of action as per our Laboratory Medical Emergency Safety Plan.

23. Auditing

The MGB performs routine internal audits of laboratories on an annual basis. The audits will be performed independent from the investigators and sponsors.

VI. Ethics and Dissemination

24. Research ethics approval

The study will be conducted in accordance with the principles of GCP. A favorable ethical opinion will be obtained from the appropriate REC and local R&D approval will be obtained prior to starting the study. The study will not start until a Clinical Trial Authorization is obtained from the appropriate Regulatory Authority.

25. Protocol amendments

Procedures defined in the study protocol will be carefully reviewed by the PI and research staff prior to the time of study initiation. Any changes to the protocol in the form of an amendment must be submitted to the IRB. We also plan to communicate important protocol modifications such as

DETAILED STUDY PROTOCOL

changes to eligibility criteria, outcomes, and analyses to trial participants, trial registry (clinicaltrials.gov), and journals.

26. Consent or assent

The research physician or physical therapist may be responsible for identifying suitable patients and obtaining consent the patient. However, the PI must confirm that the patient fulfills the eligibility criteria. The PI is responsible for ensuring informed consent is obtained before any protocol specific procedures are carried out.

27. Confidentiality

Assessment forms, reports, and other medical records must be identified in a manner that ensures participant confidentiality. All records will be kept in a secure storage area with limited access. The PI and study site staff involved with this study may not use for any purpose other than performance of the study, any data, confidential information disclosed to those individuals for the purpose of the study. Only authorized personnel will have access to these confidential files. Authorized FDA personnel have the right to inspect and copy all records pertinent to this trial. Use of study data when reporting results will be without identifiable reference to the participants.

28. Declaration of interests

There are no financial or competing interests for the PI at the start of this clinical trial.

29. Access to data

The study staff and PI will comply with the requirements of the Data Protection Act 1998 with regard to the collection, storage, processing, and disclosure of personal information and will uphold the Act's core principles. Published results will not contain any personal data that could allow identification of individual participants.

30. Ancillary and post-trial care

We will offer the care needed to treat any injury that directly results from taking part in this research study. We reserve the right to bill the participant's insurance company or other third parties, if appropriate, for the care they receive for the injury. We will try to have these costs paid for, but the participant may be responsible for some of them. For example, if the care is billed to your insurer, the participant will be responsible for payment of any deductibles and co-payments required by their insurer.

31. Dissemination policy

The clinical trial report will be used for dissemination within clinicaltrials.gov, scientific journals, and meetings. The PI has the right to publish orally or in writing the results of the study. On completion of the trial, a clinical study report will be prepared in accordance with GCP guidelines. The success of this trial depends entirely on the collaboration of a large number of doctors, therapists, neuroscientists, engineers, and other healthcare professionals. Those included in the Delegation Log will be included in any listing of collaborators. The primary trial publication will be drafted by a writing committee who will approve submission for publication.

DETAILED STUDY PROTOCOL

VII. Appendices

32. Informed consent materials

Participants will receive a copy of their signed informed consent forms.

33. Biological specimen protocols

We will collect blood samples from eligible participants by venipuncture for the purpose of accurately assessing caffeine dose, as well as C-Reactive Protein (CRP) levels. A licensed phlebotomist will draw blood using venipuncture per WHO guidelines (WHO, 2010) before and after combinatorial treatment on day one, and once after combinatorial treatment day five, totaling no more than 3 total venipuncture blood draws or 2 tablespoons of blood per time point. Collection of blood samples by venipuncture poses minimal risk to subjects. To minimize the number of venipunctures and total volume of blood drawn, we will only perform venipuncture at critical time points during the study. All samples to assess caffeine and CRP levels will be de-identified then allowed to coagulate and spun via centrifuge if needed. Serum samples will be transported to Quest Diagnostics, Inc. for analysis. Biohazard safety protocols will be strictly followed. Samples drawn to assess for additional markers will be de-identified, spun via centrifuge to extract and aliquot serum, frozen and securely stored at -80 °C until future analyses.

Blood collection protocols: To monitor caffeine plasma concentration and levels of inflammation, we collected blood samples at the beginning and end of the study visit intervention, with a total of fewer than 50mL of blood taken during a single visit day.

Genetic biomarker protocol: Subjects will participate in identifying genetic markers that may contribute to intervention responsiveness and motor recovery after SCI. Saliva samples will be collected after subjects are screened and deemed eligible to participate as defined by our inclusion and exclusion criteria. Samples will be collected using a standard passive drool protocol. The subject will be asked to collect saliva in their mouth and drool into a vial (DNA genotek OGR-500 Vials, distributed by DNA Genotek Inc, USA) via a saliva collection aide (DNA Genotek Inc, USA). The vial will be sealed tightly and stored at ambient temperature, until transported, plated, and stored at the Partners Biobank until further analysis. BDNF, ApoE, and other genotypes will be determined. The results of genotyping will be evaluated in relation to performance levels achieved following treatments. All samples will be de-identified and stored and transported according to biohazard safety protocols. Genetic testing results will not be provided to the subjects.

DETAILED STUDY PROTOCOL

VIII. REFERENCES

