or other site.¹⁹ Our study will quantify the daily (5 consecutive days) effects of caffeine (e.g., 4 mg/kg) as an adjunctive therapy to dAIH for restoring walking function in persons with chronic iSCI. This dose has known safety in iSCI and substantial antagonism to A_{2A} receptors.^{17, 20, 21}

8. Trial Design

We will conduct a placebo-controlled, cross-over, block-randomized intervention study to assess the efficacy of daily caffeine prior to AIH on improving walking function in persons with chronic, motor-incomplete SCI.

IV. Methods: Participants, interventions, and outcomes

9. Study setting

The following laboratory will be used as the primary site of this study:

INSPIRE Lab at Spaulding Hospital
[name]
[name]

10. Eligibility criteria

Potential subjects will be informed about the objectives of the study and must meet all inclusion and exclusion criteria (see Appendix 1 for sample Informed Consent Form). They will be required to read and sign approved consent and HIPAA forms prior to participation to allow access to medical information from their physicians.

Inclusion criteria: Participation requirements for SCI participants include: 1) 18 to 75 years old; 2) medically stable with medical clearance from physician to participate; 3) SCI at or below C₂ and at or above L₅ with at least some lower extremity motor function preserved below the neurologic level; 4) non-progressive etiology of spinal injury; 4) AIS A-D at initial screen; 5) at least 6 months post-injury (chronic). We plan to choose subjects greater than 6 months post-injury to ensure minimal confounding effects of spontaneous neurological recovery during the experiments. This will mean that changes in sensorimotor performance are more likely due to the interventions associated with the research study.

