Twenty individuals with chronic (> 6 months post injury), motor-incomplete SCI (i.e., American Spinal Injury Association Impairment Scale (AIS) C or D) will be recruited for the study. Prior to the start of this clinical trial, we estimated the number of participants needed to achieve study objectives. In particular, our sample size computation focused on treatments: caffeine+dAIH versus placebo+dAIH alone. Our preliminary study on the effects of caffeine prior to single AIH sequence (vs placebo+SHAM) on 10MWT showed a decrease of $2.4s \pm 1.2s$. Under the hypothesis of an additive effect of caffeine+dAIH (vs. placebo+dAIH), we anticipate the difference in walking speed (10MWT time) change between treatments would be approximately $0.06m/s$. With $N=20$ cross-over participants (includes 17% attrition rate), a repeated measures ANOVA comparing 4 treatments across 4 time points, using pooled SD of $1.3s$ across days, will be sensitive to detect a difference at power of $1 - \beta = 0.80$ ($f=0.7$, $F_{3,12}=3.5$; $p=0.4$, $\alpha=.05$).

15. Recruitment

Our study coordinator ([name]), study physicians ([name], [name]), physical therapists, PI ([name]), and research collaborators will recruit subjects using a variety of strategies shown effective in the past. First, the team will identify potential subjects using Institutional Review Board approved resources to inform persons with SCI that are currently admitted to inpatient and outpatient settings at Spaulding Rehabilitation Hospital, Boston University Medical Center, Massachusetts General Hospital, Gaylord Hospital, Albany Medical Center, and Maine Medical Center. Subjects will be recruited by word of mouth and flyers at these facilities. This project also will have access to clinical resources at Spaulding Rehabilitation Network.

Prospective participants will be contacted initially by phone or in-person and informed of the methods, inclusion/exclusion criteria, and purpose of the study. We also will provide a description of this study on ClinicalTrials.gov (NCT02323698), as required by U.S. law. In all cases, recruitment will not be coercive, will not involve undue inducements, and will accurately reflect the study.

Potential subjects will be identified by the following sources:

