Inclusion criteria: Participation requirements for SCI participants include: 1) 18 to 75 years old; 2) medically stable with medical clearance from physician to participate; 3) SCI at or below C₂ and at or above L₅ with at least some lower extremity motor function preserved below the neurologic level; 4) non-progressive etiology of spinal injury; 4) AIS A-D at initial screen; 5) at least 6 months post-injury (chronic). We plan to choose subjects greater than 6 months post-injury to ensure minimal confounding effects of spontaneous neurological recovery during the experiments. This will mean that changes in sensorimotor performance are more likely due to the interventions associated with the research study.

Exclusion criteria: Individuals will be excluded due to: 1) severe concurrent illness or pain, including unhealed decubiti, severe neuropathic or chronic pain syndrome, infection (e.g. bladder), hypertension, cardiovascular disease, pulmonary disease, severe osteoporosis (history of fractures), active heterotopic ossification in the lower extremities, or history of peripheral nerve injury in the legs; 2) < 24 on Mini-Mental Exam ²⁷; 3) severe autonomic dysreflexia; 4) history of cardiovascular/pulmonary complications; 5) pregnancy because of unknown effects of AIH on a fetus, although women of childbearing potential will not otherwise be excluded; 6) undergoing concurrent physical therapy; 7) history of diabetes. Caffeine can potentially alter sugar metabolism and, thus, persons diagnosed with diabetes will be excluded from participating in the caffeine portion of this study; 8) history of cirrhosis. Cirrhosis is known to increase the elimination time of caffeine and, thus, persons diagnosed with cirrhosis will be excluded from participating in the caffeine portion of this study; and 9) history of caffeine allergies or intolerances. Participants with a history of caffeine allergies or intolerances will be excluded from participating in the caffeine study.

Inclusion of women and minorities: We will recruit persons with SCI to include women and minorities. To protect against possible unknown side effects of dAIH, women who are pregnant may not take part in this study as the effects of dAIH on the developing fetus have not been studied. If a woman is of childbearing ability, birth control will be recommended for use throughout the study.

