26. Outcome definitions

The primary outcome measure is change in walking speed (10MWT time, s) relative to baseline (BL). For all analyses, we will use the average of two 10MWT times at BL, D₅, F₁, and F₂. Change

in walking speed will correspond to the difference between post-intervention 10MWT and BL times. Please review Table 1 for timing of outcome assessments.

All the summaries in this section will be equivalent to the main and the final results reports. There will be statistical testing completed for baseline testing of the primary outcome measure (10MWT). Since we plan to use a cross-over study design, we will compare the 10MWT baseline measurements between the interventions to evaluate the effects of the washout period.

Assessment and collection plans: Physical evaluations will be completed by the study's licensed physical therapists or occupational therapists and/or trained research study staff. Functional ability of subjects will be evaluated using standard clinical assessments with high inter-rater reliability: American Spinal Injury Association Impairment Scale (AIS) lower extremity motor scores (LEMS) to quantify strength,²⁸ and Spinal Cord Assessment Tool for Spastic Reflexes (SCATS), and the Penn Spasm Frequency Scale (PSFS) which is a self-report assessment of the frequency and severity of muscle spasms²⁹ and modified Ashworth Scale to quantify spasticity.³⁰ We also will record pain severity using the well-established Wong-Baker FACES scale, which shows high test-retest reliability and interpretability as well as good content and construct validity.^{31,32} Clinical ratings of walking ability, including Walking Index for Spinal Cord Injury (WISCI) II³³ and/or SCI Functional Ambulation Index (SCI-FAI),³⁴ will be assessed based on video recordings of the 10MWT.

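### Eligibility admits AIS A-D although the stated population is motor-incomplete (AIS C or D), and no criterion requires that a participant can complete the 10MWT on which the primary outcome rests

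*Combined protocol and SAP*

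**What the plan says.** Protocol 10 and SAP 22 carry the same inclusion list, and participants must satisfy every item.

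- **Severity.** Inclusion 4 admits "AIS A-D at initial screen".
- **Function.** Inclusion 3 asks for a lesion within a given range of levels "with at least some lower extremity motor function preserved below the neurologic level". No inclusion or exclusion item mentions standing, walking, a minimum speed or completion of a walking test.
- **Population elsewhere.** Protocol 8 and SAP 9 state the aim as "improving walking function in persons with chronic, motor-incomplete SCI". Protocol 14 and SAP 11 say that twenty people with chronic "motor-incomplete SCI (i.e., American Spinal Injury Association Impairment Scale (AIS) C or D) will be recruited for the study".
- **Outcome.** SAP 26 defines the primary outcome as change from baseline in 10MWT time in seconds. For each analysis, "we will use the average of two 10MWT times at BL", and likewise at D5, F1 and F2. Protocol 12 names the outcome as walking speed with a threshold in m/s, and Protocol 18 analyses average speed over the two trials.
- **Timing.** Protocol 11 and 13 complete enrolment and allocation at the screening visit. Table 1 first schedules the 10MWT at baseline, not at the eligibility screen.

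**The concern.** There are two separate gaps. First, the AIS range in the eligibility list contradicts the range by which the sample-size sections define the trial population. The eligibility list is the operative text, because it decides who enters. Second, the primary outcome exists only for someone who can walk 10 m, and nothing in the list secures that.

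A participant without a baseline time has no change score on the SAP's scale, and one with no time at any visit adds nothing to the mixed model. SAP 20 does not define an analysis set by a valid baseline 10MWT. SAP 28 says that the approach to missing data will be documented but gives no rule for inability to do the test. At stake are the evaluable sample size in a 20-person trial and the match between the people enrolled and the population named in the conclusion.

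**Working it through.** **1. AIS grades side by side.** The eligibility lists (Protocol 10, SAP 22) admit A, B, C and D. The sample-size sections (Protocol 14, SAP 11) name C or D. Grades A and B are therefore admitted by the list and lie outside the population as defined elsewhere. Inclusion 3 removes some people with grades A and B, but the documents do not say how many.

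**2. Does any criterion secure a 10MWT value?** Inclusion 3 requires only some preserved leg motor function, which does not ensure a 10 m walk. Grade C or D is not defined by walking either, so correcting the AIS range alone would not close this gap.

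**3. The plan's own sample size.** Inputs from Protocol 14 and SAP 11: N = 20 including 17% attrition, 4 treatments, 4 time points, f = 0.7, F(3,12) = 3.5, alpha 0.05, power 0.80. The stated p = 0.4 is taken to be the correlation between repeated measures; this is an assumption.

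- Twelve denominator degrees of freedom with 4 groups imply 12 + 4 = 16 evaluable. The 5% critical value of F(3,12) is 3.49, which matches 3.5.
- 16 / (1 − 0.17) = 19.3, rounded up to 20. The stated N is reproduced.
- Noncentrality: λ = f² × n × m / (1 + (m − 1)ρ) = 0.49 × 16 × 4 / 2.2 = 14.25. Power at n = 16 is 0.773, a little under the stated 0.80. With f = 0.72, which rounds to 0.7, it is 0.798. At f = 0.70, the smallest n reaching 0.80 is 17 (power 0.810).
- 20 × 0.83 = 16.6, so ordinary attrition already takes the evaluable number down to the 16 that the calculation needs.

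**4. Effect of participants without a 10MWT.** Let k of the 20 have no value, with 17% attrition among the rest, so n = (20 − k) × 0.83, rounded down. The values of k are assumed.

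| k of 20 | n before rounding | n used | λ | Power |
|---|---|---|---|---|
| 0 | 16.60 | 16 | 14.25 | 0.77 |
| 2 | 14.94 | 14 | 12.47 | 0.68 |
| 4 | 13.28 | 13 | 11.58 | 0.62 |
| 6 | 11.62 | 11 | 9.80 | 0.50 |

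Rounding to the nearest whole person instead gives n = 17, 15, 13 and 12, with power 0.81, 0.73, 0.62 and 0.56. The pattern is the same.

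**5. Check on a simpler model.** A paired t-test with 80% power at n = 16 has a standardised difference of 0.75. At n = 14, 13 and 11 its power is 0.74, 0.70 and 0.61.

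**6. Enrolment needed to keep 16 evaluable.** 16 / (0.83 × (1 − q)), rounded up, is 22, 25 and 28 when a share q of 10%, 20% and 30% has no 10MWT.

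**The case against.** Several points on the other side are sound.

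- A reader might infer that the trial is defined and analysed for walkers. The documents do not say so: no section requires ambulation, and the analysis sections set no AIS restriction. The need to walk is inferred from the outcome and from procedures such as walking practice, the TUG and the 6MWT. Those procedures also make heavy enrolment of non-walkers less likely.
- A reader might count two of four admitted grades as out of scope and conclude that the problem is of that size. Inclusion 3 narrows entry for grades A and B by an unknown amount, so counting grades says nothing about the number of people.
- A reader might suppose that a few non-walkers would exhaust the attrition allowance of about 3.4 people (20 − 16.6). No count of non-walkers has a source in the documents.
- A reader might treat loss from the primary model as certain. It follows on the SAP's time scale. On the speed scale of Protocol 12 and 18, inability could be scored as 0 m/s. No rule says that it would be, so the handling is unsettled, not resolved.
- A reader might suspect bias towards one intervention. Each participant is meant to receive all three, so someone who cannot walk throughout contributes no time to any of them. The cost is mainly precision.

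None of this removes the contradiction in the AIS range or supplies the missing criterion.

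**Conclusion.** The concern holds in two parts. The AIS mismatch is a direct contradiction, present in both protocol and SAP, and needs no assumption. The missing 10MWT requirement is established by reading the complete eligibility lists against the SAP's outcome definition. Together they allow people outside the stated population, or without a baseline 10MWT time, to be enrolled and allocated.

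The size is conditional. If 2 to 6 of 20 had no 10MWT, on top of 17% attrition, power on the plan's model would fall from about 0.77 to between 0.68 and 0.50. This rests on the assumed counts, on reading 0.4 as a correlation, and on a power model with four treatments and between-group degrees of freedom, whereas the trial crosses over three interventions. The figures are therefore illustrative.

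**What to change.** 1. Reconcile the AIS range across Protocol 8, 10 and 14 and SAP 9, 11 and 22, so that the eligibility list matches the stated motor-incomplete population.
2. Add to the inclusion lists in Protocol 10 and SAP 22 that the participant can complete the 10MWT at screening, before allocation, using the least restrictive assistive device, the term that SAP 26 already uses for the walking assessments.

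Both edits are needed, since neither does the work of the other. They fit in one eligibility amendment and leave N = 20 unchanged. The downside is a slightly smaller recruitment pool. Parts of Protocol 10 and SAP 22 describe recruitment in the past tense. If enrolment has begun, the amendment cannot reach people already entered, and the report should give their AIS grades and the number without a baseline 10MWT.
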